7.2.2 EXAMPLE: Visit 2 or Day 2 or Post-test, etc. (format accordingly)

On Labor and Delivery will have continuous fetal heart rate and tocodynamometer monitoring. During misoprostol administration provider will perform sterile vaginal exams every 4 hours (range 4-5 hours). After misoprostol administration is completed, provider will perform sterile vaginal exams every 2 hours (range 1-3 hours). Nurse or provider will document every 2 hours if patient subjectively states they are nauseated or have had diarrhea. Nurse or provider will document the amount of times anti-emetics were administered. Subject's vital signs will be taken every hour as routine protocol at Hershey Medical Center. It will be noted if there is meconium stained amniotic fluid. Umbilical cord gases will be obtained on every subject.

7.3 Duration of Participation

The time it takes for the subject's initiation of induction of labor to delivery of infant.

7.4 Test Article(s) (Study Drug(s) and/or Study Device(s))

7.4.1 Description

Misoprostol is currently available in 100 mcg tablets. The 100 mcg tablet will be divided into 4 equal pieces to become a 25 mcg tablet. The 25 mcg tablet will be used for the study. There is a small margin of error in creating an exactly 25 mcg tablet since there are no scores on the 100 mcg tablet. When dividing the 100 mcg tablet into four pieces, if any of the ¼ tablets judged to appear uneven based on weight they will be discharged at time of preparation. To assist in this judgment, pharmacy will weigh 10 tablets of misoprostol to calculate what an average ¼ piece should weigh. If a ¼ tablet weighs 5% greater difference than what it's estimated weight should be, it will be discarded. If all 4 pieces appear appropriately sized they will be used. Misoprostol was originally approved by the FDA for reducing the risk of NSAID induced gastric ulcers. It does have a black box warning against its use in pregnancy, but then in 2002 had a new label stating

its use during pregnancy for cervical ripening and induction of labor. [1] The American Congress of Obstetricians and Gynecologists (ACOG) have also supported the use of misoprostol that it is a safe and effective form of cervical ripening and induction of labor. [2]

7.4.2 Treatment Regimen

Subject with either receive misoprostol 25 mcg by mouth every 2 hours (range 2-3 hours) or misoprostol 25 mcg per vagina every 4 hours (range 4-5 hours). The dosing and protocol for each treatment arm is further described in Section 7.1 Study Design.

7.4.3 Method for Assigning Subject to Treatment Groups

The randomization scheme for this study will use variable-size, random permuted blocks to ensure that the number of participants in each treatment arm is balanced after each set of B randomized participants, where B is the block size. Furthermore, the randomization will be stratified by whether the participant is nulliparous or multiparous. A randomization order will be made for oral or vaginal misoprostol through REDCap software. After meeting eligibility criteria and being consented for the study, a subject will be ready to be randomized. Team members that have REDCap access with access REDCap to carry out the randomization assignment. If they do not have access, and a fellow team member is present with access to REDCap, the fellow team member will carry out the randomization assignment. If no team member is available with REDCap access the Co-PI will be contacted and will enter the relevant subject information into REDCap and REDCap will return a randomization assignment. The randomization will then be relayed to the study team member to carry out the assigned randomization. If co-PI is not available, the PI ([name]) will be contacted to enter the subject's relevant information into REDCap and receive a randomization assignment. If REDCap is offline and unavailable at the time of randomization, or the co-PI and [name] were not able to be contacted, Investigational Drug Services Pharmacy at Penn State Hershey Medical Center will have randomization assignments on paper as a backup hardcopy in order to randomize a patient.

7.4.4 Subject Compliance Monitoring

When the medication is administered, a registered nurse will administer the oral misoprostol and a physician will administer the vaginal misoprostol, for which both medications will be properly documented as of their time of administration by nursing.

7.4.5 Blinding of the Test Article

There will be no blinding in this study.

7.4.6 Receiving, Storage, Dispensing and Return

7.4.6.1 Receipt of Test Article

The misoprostol tablets will be obtained, prepared, dispensed, returned and destroyed by Investigational Drug Services Pharmacy at Penn State Hershey Medical Center. Misoprostol 100mcg tablets will be purchased from a pharmacy distributor. The Investigational Pharmacy will divide the 100mcg tablet into four pieces under a vertical laminar flow hood and then unit dose the 25mcg $\frac{1}{4}$ tablets. Each quarter tablet that was produced from the splitting will be weighted and the weight will be recorded. Any $\frac{1}{4}$ tablets judged to be uneven will be discarded at the time of preparation. To assist in this judgment, pharmacy will weigh 10 tablets of misoprostol to calculate what an average $\frac{1}{4}$ piece should weigh. If a $\frac{1}{4}$ tablet weighs 5% greater difference than what it's estimated weight should be, it will be discarded. If all 4 pieces appear appropriately sized they will be used.

7.4.6.2 Storage

Prepared misoprostol doses will be stored at controlled room temperature with other inpatient investigational medications in Penn State Hershey Medical Center Pharmacy. The Investigational Pharmacy will be responsible for maintaining and managing the storage, preparation, dispensation, and destruction of the misoprostol for this study following their standard operating procedures.

7.4.6.3 Preparation and Dispensing

The Investigational Pharmacy will divide the 100mcg misoprostol tablet into four pieces under a hood and then unit dose the 25mcg ¼ tablets. Each quarter tablet that was produced from the splitting will be weighed and the weight will be recorded. Any ¼ tablets judged to be uneven will be discarded at the time of preparation. To assist in this judgment, pharmacy will weigh 10 tablets of misoprostol to calculate what an average ¼ piece should weigh. If a ¼ tablet weighs 5% greater difference than what it's estimated weight should be, it will be discarded. If all 4 pieces appear appropriately sized they will be used. Pharmacy will dispense six ¼ tablets labeled for the specific subject at a time. For subjects randomized to receive oral administration of misoprostol, six additional ¼ tablets may be dispensed as needed. The prepared misoprostol ¼ tablets (=25mcg) will be the same in both administration arms. Randomization ordering will determine whether the subject receives misoprostol orally administered by the registered nurse or vaginally placed by the physician.

7.4.6.4 Return or Destruction of the Test Article

Misoprostol will be dispensed by pharmacy following receipt of a written study order. Any unused tablets will be returned to pharmacy. Pharmacy will be responsible for proper destruction of the product when applicable.

7.4.6.5 Prior and Concomitant Therapy

Any medication therapy that is required by the subject for their medical history or labor course is permitted during the study. If the subject receives magnesium sulfate for seizure prophylaxis due to preeclampsia during their labor course, that subject will be accounted for in an intent to treat analysis.

8.0 Subject Numbers and Statistical Plan

8.1 Number of Subjects

A total of 110 subjects will be randomized.

From looking at previous data collected at Penn State Hershey Medical Center, there were about 350 induction of labors using misoprostol over one year's time. Due to inclusion/exclusion criteria it is estimated that only 60% of the induction of labors will qualify for the study. That leaves about 210 patients able to participate in the study. Potentially the study could be completed within six months.

8.2 Sample size determination

With respect to the primary study endpoint of the time interval from administration of misoprostol to active phase of labor (greater than or equal to 6 cm dilation), shorter times are considered better. Based on a previous published data, the mean time interval from vaginal misoprostol administration to active phase of labor was 12.0 hours (standard deviation (SD)=5.9 hours) [9] and the mean time interval from oral misoprostol administration to active phase of labor was 9.9 hours (SD=7.1 hours). [10] Using these standard deviations and a non-inferiority margin of 4 hours, a sample size of 92 patients (46 per group) would provide 80% power to

detect non-inferiority of oral misoprostol compared to vaginal misoprostol with respect to the time interval from administration of misoprostol to active phase of labor using a one-sided Mann-Whitney test having a significance level of 0.025. Factoring in a 15% drop-out rate, our target sample size is 110 subjects.

8.3 Statistical methods

Analyses will invoke an intent-to-treat paradigm, wherein all randomized subjects are included according to their randomized treatment arm, regardless of actual treatment received. Data will be summarized using descriptive statistics for continuous variables (mean, standard deviation, number of observations, and percentiles) and frequency statistics (frequencies and percentages) for categorical variables. Univariate and bivariate distributions will be inspected in order to address any missing data, inconsistent responses, outliers, and data entry errors.

The primary study endpoint will be the time interval from administration of misoprostol to active phase of labor (greater than or equal to 6 cm dilation) and shorter time is considered better. The difference between the treatment arms (oral misoprostol – vaginal misoprostol) will be denoted by Δ and the non-inferiority margin will be set to $\delta=4$ hours. Thus to test for non-inferiority of oral misoprostol compared to vaginal misoprostol the null hypothesis is $H_0: \Delta \geq 4$ hours and the alternative hypothesis is $H_a: \Delta < 4$ hours. The distribution of the time interval from administration of misoprostol to active phase of labor (greater than or equal to 6 cm dilation) is expected to be skewed. Therefore, to test for non-inferiority of oral misoprostol compared to vaginal misoprostol with respect to the primary endpoint, a one-sided Mann-Whitney test will be used where the non-inferiority margin will be set to 4 hours. The upper bound of the one-sided 97.5% confidence interval for testing non-inferiority will be constructed using the Mann-Whitney test as described by Rothman et al. [11] If the upper bound of the one-sided 97.5% confidence interval is less than the non-inferiority margin of 4 hours, then the null hypothesis will be rejected. In the event the primary endpoint is normally distributed, a one-sided, two-sample t-test will be utilized to test for non-inferiority with corresponding one-sided 97.5% confidence interval.

As detailed in Section 1.3, there are numerous secondary endpoints for this study. Secondary continuous outcomes (e.g., time interval from administration of misoprostol to initiation of oxytocin for continued augmentation of labor and time interval from administration of misoprostol to vaginal delivery) will be compared between the two treatment groups using a two-sample t-test or Mann-Whitney test, as appropriate, based on the distribution of the outcome. Additionally, as a secondary analysis, Kaplan-Meier survival curves will be constructed for these two time to event outcomes. Secondary categorical outcomes (e.g., Section 1.3 secondary endpoints 3-15 which includes Cesarean section rate and rate of tachysystole) will be compared between the two groups using a chi-square test (or Fisher's exact test if the expected cell counts are small).

While every attempt will be made to collect complete data and prevent participant drop-out, there is the possibility of drop-outs and other missed information. We expect the underlying mechanism of any missing data for this particular study to arise due to data that are missing-at-random (MAR). One reason the MAR assumption is expected for this study is because the two treatment arms are providing the same drug (misoprostol) but via different routes (oral vs. vaginal). The statistical methods and analyses that are planned for the primary and secondary outcomes are appropriate, and provide valid inference, under the MAR assumption. Although not expected for this study, if it appears the MAR assumption is not reasonable then we will use multiple imputation to handle the issue of missing data for analyses.

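### Randomization is stratified by parity, but the primary test, its 97.5% bound and the t-test fallback ignore parity: a cheap gain in precision is left unused

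*Combined protocol and SAP*

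**What the plan says.** Section 7.4.3 uses permuted blocks and adds that "the randomization will be stratified by whether the participant is nulliparous or multiparous". Section 8.2 sizes the trial "using a one-sided Mann-Whitney test having a significance level of 0.025", with SDs of 5.9 h (vaginal) and 7.1 h (oral), a 4 h margin and 80% power. That gives 46 per group, raised to 110 in total for 15% drop-out.

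For the primary endpoint, section 8.3 states that "a one-sided Mann-Whitney test will be used where the non-inferiority margin will be set to 4 hours". On the bound: "The upper bound of the one-sided 97.5% confidence interval for testing non-inferiority will be constructed using the Mann-Whitney test". If the endpoint turns out to be normal, "a one-sided, two-sample t-test will be utilized to test for non-inferiority with corresponding one-sided 97.5% confidence interval". Sections 8.2 and 8.3 do not mention parity, and no stratified, adjusted or parity sensitivity analysis is planned.

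The target is named only in general terms: "The difference between the treatment arms (oral misoprostol – vaginal misoprostol) will be denoted by" Δ. Section 8.2 starts from means ("the mean time interval from vaginal misoprostol administration to active phase of labor was 12.0 hours"), while section 8.3 expects a skewed distribution and plans a rank test. Whether 4 h is a location shift or a mean difference is not stated.

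**The concern.** Balancing the arms within parity groups removes parity as a source of chance difference between them. An unstratified test does not know this: the spread it uses still contains the variation between nulliparous and multiparous women. If that variation is large, the test rejects less often than its nominal level allows, and the upper bound sits higher than the data require. Section 8.3 decides non-inferiority by whether that bound is below 4 h, so any loss falls on the primary conclusion of a trial planned at 80% power.

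**Working it through.** **Inputs.** From section 8.2: SDs 5.9 and 7.1 h, margin 4 h, one-sided alpha 0.025, power 80%, 46 per group, 15% drop-out. From section 7.4.3: balance of arms within parity. Assumed, because the documents do not give them: the parity gap (difference in mean time to 6 cm between the two parity groups), 23 + 23 women per arm, the shape of the distribution, the same treatment effect in both strata, and an observed endpoint for everyone.

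**The plan's own figure.** Average variance = (5.9² + 7.1²)/2 = (34.81 + 50.41)/2 = 42.6, so SD = 6.53. With a true difference of 0, n per arm = 2 × 42.6 × (1.960 + 0.842)²/4² = 41.8, so 42; the noncentral t gives 43. Dividing by the Mann-Whitney efficiency 3/π = 0.955 gives 45.03, so 46 per arm and 92 in all. Drop-out: 92/0.85 = 108.2, so 109, or 110 as an even number. Both stated figures reproduce.

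**Variance explained by parity.** With equal strata the share is (gap²/4)/42.6: 1/42.6 = 2% at 2 h, 4/42.6 = 9% at 4 h, 9/42.6 = 21% at 6 h, 16/42.6 = 38% at 8 h.

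**Simulation, normal data.** Total SDs were held at 5.9/7.1, with 80,000 runs per setting (Monte Carlo SE about 0.0006 at alpha 0.025). Power is at a true difference of 0; alpha is at a true difference of 4 h.

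| Parity gap (h) | Mann-Whitney power | van Elteren power | t-test power | Linear model (arm, parity) power | Mann-Whitney alpha |
|---|---|---|---|---|---|
| 0 | 80.9% | 80.2% | 82.8% | 82.8% | 0.025 |
| 2 | 81.3% | 81.3% | 83.2% | 83.9% | 0.024 |
| 4 | 81.9% | 83.9% | 83.8% | 86.1% | 0.020 |
| 6 | 83.0% | 88.4% | 85.3% | 90.4% | 0.014 |
| 8 | 85.0% | 94.4% | 88.1% | 95.7% | 0.007 |

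The rank-test gain is 83.9 − 81.9 = 2.0 points at 4 h and 88.4 − 83.0 = 5.4 at 6 h. In a separate run with a common SD of 6.53, van Elteren alpha stayed at 0.024–0.026 while parity explained 0 to 30% of the variance.

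**Skewed data, pure shift** (gamma shape 4, SD 6.53 in both arms). Van Elteren alpha is 0.024–0.025. Power goes from 87.2% to 89.8% at 4 h (2.6 points) and from 87.4% to 93.5% at 6 h (6.1 points).

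**Skewed data, SDs 5.9/7.1** (gamma shape 4). Here a shift and a mean difference part company: a within-stratum location shift of 4 h corresponds to a mean difference of 4.30–4.37 h.

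| Alpha at gap 0 / 4 / 6 / 8 h | Margin = mean difference | Margin = within-stratum location shift |
|---|---|---|
| Unstratified Mann-Whitney | 0.043 / 0.033 / 0.020 / 0.009 | 0.025 / 0.017 / 0.011 / 0.003 |
| van Elteren | 0.042 / 0.045 / 0.048 / 0.056 | 0.024–0.026 |
| Linear model (arm, parity) | 0.027–0.029 | not computed |

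Power in this setting is 90.0% unstratified against 92.2% van Elteren at 4 h, and 89.7% against 94.9% at 6 h. These gains (2.2 and 5.2 points) compare tests that hold 0.025 only under the location-shift reading.

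**Mean upper bound, unstratified against stratified** (5,000 runs). Normal: 2.73 and 2.76 h at gap 0, 2.76 and 2.65 h at 4 h, 2.77 and 2.47 h at 6 h. Skewed, SDs 5.9/7.1: 2.29 and 2.32 h, 2.33 and 2.14 h, 2.47 and 2.00 h.

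**Parity mix.** With 28 and 18 women per stratum in each arm (skewed, SDs 5.9/7.1), power is 90.1% against 92.3% at 4 h and 90.0% against 94.9% at 6 h, so the mix matters little.

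**The case against.** The trial was sized for the unstratified test, and that test's power stays at or above 80% at every gap examined. An unadjusted primary test after stratified randomization is a defensible choice. The size of any loss rests wholly on assumptions, and at a 4 h gap the mean bound moves by only 2.76 − 2.65 = 0.11 h (normal) or 2.33 − 2.14 = 0.19 h (skewed). All of this stands and sets the weight of the point.

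Two further objections stand in part. What the margin means is a separate question: at gap 0, where parity is irrelevant, the planned test already has alpha of about 0.04 for a 4 h mean difference with skew and unequal SDs. It has to be answered here all the same, because the stratified test holds its level under one reading and not the other. And under the mean-difference reading with skew, moving to van Elteren raises alpha (0.033 to 0.045 at 4 h). The linear model is no free substitute: with skewed data its power at 4 h is 85.5%, against 90.0% for the planned test, though part of that difference reflects the rank tests' higher alpha.

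A reader might infer that ignoring the stratification factor invalidates the primary test or leaves the trial short of power. The documents support neither: the sample size reproduces for the test as planned. A reader might also infer that the unstratified test is always conservative. It is so for normal data or a location-shift margin, but not always for a mean-difference margin under the skew that section 8.3 expects. Nor should the point be carried over to the secondary comparisons, for which no consequence has been shown.

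**Conclusion.** The point holds as a cheap improvement, not as a correction. The primary test, its bound and the t-test fallback leave out the factor used to stratify randomization. If parity predicts time to 6 cm, the bound is wider than needed. Where both tests keep to 0.025, stratifying adds no power at a gap of 0–2 h, about 2–3 points at 4 h and about 5–6 points at 6 h.

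These figures assume the parity gap, a 50:50 mix, a common treatment effect across strata and complete endpoint times. Women delivered before 6 cm would have no observed time, so the decimals should not be read as precision. Confidence in the size is medium; the omission itself is plain from the text.

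**What to change.** In section 8.3:

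1. State that the 4 h margin is a within-stratum location shift. This matches the Mann-Whitney bound already planned.
2. Make the parity-stratified version of the planned test primary: van Elteren on oral times shifted by 4 h, with the one-sided 97.5% Hodges-Lehmann upper bound obtained by inverting that test.
3. In the normal branch, replace the two-sample t-test with a linear model with arm and parity.
4. Keep the unstratified Mann-Whitney as a sensitivity analysis, and report the linear model with arm and parity as a supportive mean-difference analysis in all cases.

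**Cost.** No new data, since parity is recorded at randomization. The stratified bound must be written out, because section 8.3 cites a method for the Mann-Whitney bound only. If parity has no effect, about half a point of power is lost (80.9 − 80.2 = 0.7 normal; 90.0 − 89.5 = 0.5 skewed). With skew and unequal SDs, van Elteren does not hold 0.025 for a 4 h mean difference (0.042–0.056 at gamma shape 4; 0.053–0.084 with the stronger skew of gamma shape 2). The linear model (0.027–0.029 and 0.027–0.031 respectively) is the check on that reading. The choice should be fixed before outcomes are compared, because the trial is open-label.

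### Section 8.3 wrongly calls its unadjusted tests valid under MAR, reserves multiple imputation for when MAR fails, and gives no rule for women delivered before 6 cm

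*Combined protocol and SAP*

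**What the plan says.** The primary endpoint (section 1.2) is the time from misoprostol to at least 6 cm. Section 8.3 analyzes by intention to treat, "wherein all randomized subjects are included according to their randomized treatment arm", and "a one-sided Mann-Whitney test will be used where the non-inferiority margin will be set to 4 hours". A t-test replaces it if the times look normal. Neither test has a covariate or handles censoring.

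On missing data, section 8.3 says "Univariate and bivariate distributions will be inspected in order to address any missing data". It then expects MAR and states: "The statistical methods and analyses that are planned for the primary and secondary outcomes are appropriate, and provide valid inference, under the MAR assumption". The ground offered begins "One reason the MAR assumption is expected for this study is because the two treatment arms are providing the same drug (misoprostol" and adds that only the route differs. The fallback is: "if it appears the MAR assumption is not reasonable then we will use multiple imputation to handle the issue of missing data for analyses". No type of imputation is named.

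The only method that could handle censoring is confined to time to oxytocin and time to vaginal delivery: "Kaplan-Meier survival curves will be constructed for these two time to event outcomes". Randomization is stratified by parity (section 7.4.3). Section 3.3.2 lets chart data of withdrawn women be used.

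**The concern.** Two statements are wrong as written.

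- A covariate-free test on observed times is not valid under MAR in general. It holds if missingness depends on arm alone, or on parity equally in both arms. It fails if missingness depends on arm and parity jointly and parity predicts the time.
- Standard multiple imputation assumes MAR, so calling on it only when MAR fails does not repair that failure. Giving the same drug by another route says nothing about why a time would be missing.

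The related gap concerns women who never have a time. Section 7.1 lets the provider move to delivery after repeated Category II tracings, and hands Category III tracings to the primary team. A woman delivered before 6 cm has no endpoint value, and a chart cannot supply an event that did not occur. Section 8.3 requires her in the analysis without saying whether she is omitted, censored or ranked last. At stake is whether the non-inferiority result depends on a choice made after the data are in, in a trial with no blinding (section 7.4.5).

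**Working it through.** **1. The plan's own figure.** Inputs from section 8.2: SDs 5.9 h (vaginal) and 7.1 h (oral), margin 4 h, one-sided 0.025, power 80%; true difference taken as 0. Pooled SD = √((5.9² + 7.1²)/2) = √42.61 = 6.53 h. A t-test needs 43 per arm. Allowing for Mann-Whitney efficiency, 43 × π/3 = 45.03, so 46 per arm and 92 in all. 92/0.85 = 108.2, so 109 against the planned 110. The size reproduces and is not in question.

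**2. Why MAR is not enough.** Assume 60% nulliparous, with mean times 14 h and 9 h by parity: 0.6 × 14 + 0.4 × 9 = 12.0 h, the vaginal mean in section 8.2. Let loss depend only on arm and parity, at rates *a* (nulliparous) and *b* (multiparous). The nulliparous share of observed women is s = 0.6(1−a)/[0.6(1−a) + 0.4(1−b)], and the observed mean, before any arm effect, is 9 + 5s. For 25/0 in the oral arm, s = 0.45/0.85 = 0.529 and the mean is 11.65 h.

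The last column is simulated: 55 per arm, 10,000 replicates, true difference 4 h, parity exactly balanced.

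| Loss % (nulliparous/multiparous), oral vs vaginal | Overall loss %, oral/vaginal | Observed mean (h), oral/vaginal | Bias (h) | One-sided error |
|---|---|---|---|---|
| 20/5 vs 5/5 | 14/5 | 11.79/12.00 | −0.21 | 2.4% |
| 25/5 vs 10/5 | 17/8 | 11.71/11.93 | −0.22 | 2.6% |
| 25/0 vs 5/5 | 15/5 | 11.65/12.00 | −0.35 | 3.2% |
| 15/5 in both | 11/11 | 11.87/11.87 | 0 | 1.4% |
| 10/5 vs 25/5 | 8/17 | 11.93/11.71 | +0.22 | 0.8% |

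With full data the error is 1.2–1.4%. It lies below 2.5% because the test ignores a predictor that the design has balanced. A separate simulation put the top of the range at 3.3%. The Monte Carlo standard error near 2.5% is √(0.025 × 0.975/10,000) = 0.16 points.

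**3. What imputation repairs.** Twenty normal imputations within arm and parity, with Rubin's rules on the mean difference (4,000 replicates, parity balanced), give 1.5–1.8% under parity-related MAR loss. If instead labors longer than 24 h are lost, which is not MAR, imputation gives 6.4%, against 7.4% for the observed-times t-test and 1.6% with full data. Imputation helps where the plan withholds it and does little where the plan calls on it.

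**4. Delivery before 6 cm.** 55 per arm, gamma times (mean 12 h, SD 5.9 h), oral shifted by 4 h, 10,000 replicates. With no loss the Mann-Whitney error is 2.5%. All loss rates are assumed.

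| Assumed loss (oral/vaginal) | Error if omitted |
|---|---|
| Unrelated to speed, 5%, 10%, 15% in both arms | 2.6%, 2.4%, 2.3% |
| Unrelated to speed, 5%/10% | 2.5% |
| Lost after 24 h (9.8%/4.0%) | 6.9% |
| Lost after 27 h (5.1%/2.0%) | 4.9% |
| Lost after 30 h (2.5%/0.9%) | 3.1% |
| Lost after 36 h (0.6%/0.2%) | 2.7% |
| Hazard 0.05/h after 12 h (18.3%/9.4%) | 5.8% |
| Hazard 0.05/h after 18 h (6.3%/2.7%) | 4.7% |
| Slowest 5% or 10%, vaginal arm only | 0.8%, 0.2% |

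A separate simulation gave 4–8% when slow labors are lost on a common clock, so 3–8% is a fair bracket.

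Ranking these women last is not safe everywhere either: it gives 6.7% error for time when loss unrelated to speed is 5% oral and 10% vaginal. With equal routes and 10% random loss, omission and last rank disagree in 11.5% of trials (gamma) or 17.2% (normal times with the planning SDs). Most of these (10.6 and 15.2 points) are last rank missing a true non-inferiority.

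**The case against.** The best defense is that a default can be read into the plan. Section 8.2 says "Factoring in a 15% drop-out rate, our target sample size is 110 subjects" and section 8.3 holds imputation back, so analysis of observed times seems intended. That is probably right, but it is not written, and it conflicts with including every randomized woman.

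Second, the MAR error in this design stays close to nominal. This stands. A reader might infer a larger effect from runs with parity left to chance (3.9–4.8%), but section 7.4.3 stratifies by parity, so those runs do not describe this trial. Truly missing times may also be few, given section 3.3.2.

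Third, the routes to early delivery in section 7.1 follow fetal tracings, and nothing there ties them to slow labor. Mechanical dilation is what opens at 24 h, so 24 h is not a delivery deadline and the figure for that cutoff is an upper case. This also stands.

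Fourth, multiple imputation can be built for data not MAR, for example with a delta shift. It can, but section 8.3 names no such form.

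Fifth, the imputation runs tested a mean difference, not the planned Mann-Whitney bound. This limits what they show and shapes the fix.

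**Conclusion.** Both statements in section 8.3 are wrong as written, and the rule for delivery before 6 cm is missing. Confidence in these is high.

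Confidence in the size is low to moderate, because every loss rate and the parity gap are assumed. Under those assumptions, parity-related MAR loss roughly doubles the one-sided error, from 1.2–1.4% to 2.4–3.3%, which remains near 2.5%. Omitting women delivered before 6 cm ranges from conservative, through neutral, to about 3–8%, depending on who is lost.

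Two stronger readings are not supported. A reader might infer that the plan favors non-inferiority. The documents give no rate of delivery before 6 cm, and section 5.1.1.2 cites the lowest cesarean rate for oral misoprostol, so the direction is unknown. A reader might also infer from section 10.6 that the six-monthly review exposes the primary endpoint by arm. Sections 10.5 and 10.7 describe adverse events, early termination and accrual. The open label is reason enough to fix the rule in advance.

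**What to change.** 1. Delete the sentence claiming validity under MAR. For genuinely missing times, make multiple imputation with arm and parity (and baseline Bishop score if recorded) the MAR analysis. Use an imputation model suited to skewed times, and state how the Mann-Whitney shift estimate and its 97.5% bound are pooled. Name a delta-adjusted or tipping-point analysis for when MAR is doubted.
2. Treat delivery before 6 cm as an event with its own rule, fixed before any comparison of the primary endpoint by arm. Say whether the primary test uses observed times or ranks these women last. Pre-specify the other as a sensitivity analysis, so that one of the two keeps all randomized women, and report counts by arm. Make the all-randomized sentence agree with the choice. Observed times confine the result to women who reach 6 cm. Last rank costs power: 70% against 84% with equal routes, the planning SDs and 10% random loss.

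Cost: wording, one imputation analysis with its delta-adjusted companion, one sensitivity analysis and one table, on data already being collected, with no change in sample size. The downside is that a non-inferiority claim may look less robust if the two analyses disagree.
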